Research Design and Methods: All human subjects' research will be conducted with full approval from the IRB at the University of Texas Health Science at Houston. We will recruit PND patients (N=10) who will be administered a single intravenous infusion of Ketamine either at 0.5 mg/kg or 0.2 mg/kg over 40 minutes in a double-blinded and crossover fashion separated by minimum 7 days, with the order being randomized and balanced across subjects. Two doses will help decide the safe, tolerable and effective dose for PND subjects will undergo a standard screening interview visit to confirm eligibility evaluations including SCID-4 interview (27) and collection of demographic, clinical and medical history. To ensure medical stability, each patient will have a physical examination and urine toxicology screen to rule out the recent undisclosed use of illicit substances. It will also be requested that the patient provide a record of lab results to indicate adequate health for inclusion.

We will pre-screen potential participants over the phone to minimize the invitation to non-eligible participants. Eligible patients that want to participate in the study will be scheduled to have a screening visit to review consent and determine eligibility.

The total duration of the commitment of the study is minimum of 4 weeks. Extension of the timeline can occur depending on the time between the screening visit and the first infusion dose. The total commitment should not exceed 3 months. There will be a minimum 7 days between the 2 infusions. Patients who qualify will complete the infusions on another day at UTHealth Clinical Research Unit at Memorial Hermann-TMC, Houston. University of Texas Health Science Center at Houston Memorial Hermann-TMC [name] or at our Harris County Psychiatric Center (HCPC) where they will be given the ketamine infusion by the study nurse. Patients will be advised to follow the American Association Preoperative Fasting Guidelines prior to infusion.

There will be two appointments where they will be administered a single intravenous infusion of Ketamine either at 0.5 mg/kg or 0.2 mg/kg over 40 minutes in the first infusion visit and a second infusion visit where they will receive the infusion that was not given on the first visit, where there will be a minimum of 7 days between infusions.

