DATA ANALYSIS PLAN - General Data Analysis: The data analytic strategy will use generalized linear modeling. Statistical analyses will use SAS v.9.3. Preliminary data analyses will inspect baseline, treatment from baseline differences as well as correlations between baseline variables and specified outcomes. Baseline characteristics will be compared within groups using Student's t-tests for continuous data and chi-square tests for categorical data.

Sample size justification: our power calculation is guided by a previous study - intravenous ketamine in TRD patients (28) with effect size (Cohen's $d = 1.46$) or Brexanolone in PND (effect size 1.2) (12, 32). For an effect size 1.2, a total of 10 PND patients will be required for within-subject design with probability 95 % that the study will detect a treatment difference at a one-sided 0.05 significance level.

Hypothesis: Based on previous studies (33, 34) and our pilot Ketamine TRD patient data, we predict that ketamine infusion compared to baseline will significantly decrease HAM-D scores in PND patient at 24 hrs. The severe anxious subtype will have prominent improvement.

Analysis: We will use linear regression to assess associations between improvements in depressive symptoms (change in the HAM-D from baseline using LOCF). A paired t-test was performed to evaluate the key efficacy measure - change from baseline in HAMD total score. We will also perform a secondary analysis comparing change from baseline to endpoint using last observation carried forward (LOCF) using a paired sample t-test. Secondary outcomes are safety and tolerability measures, including treatment-emergent AEs and changes from EPDS, GAD-7, PHQ-9, and C-SSRS. We will also investigate specific markers for treatment response.

Alternate plans: The proposal applies the widely used ketamine sub-anesthetic dose (0.5 mg/kg) as a treatment for PND. If the effect is less clear or patient experiences any adverse effects, alternate strategies will be explored (two doses of ketamine instead of single or low dose 0.3 mg/kg if adverse effects etc. respectively). Patient safety and tolerability will be the most important guiding principle. This will require an amendment in the protocol and an updated consent.

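### The analysis plan defines no unit of analysis for its two-infusion crossover, gives its models no patient, period or sequence term, and names no within-patient test of the dose hypothesis

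*Combined protocol and SAP*

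**What the plan says.** **Design.** METHODS, Research Design and Methods, gives each of 10 patients both doses "in a double-blinded and crossover fashion separated by minimum 7 days, with the order being randomized and balanced across subjects". The assessment table schedules HAM-D-17 before and after each infusion and at the day-1 call after each, so each patient yields two change scores at 24 hours.

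**Hypotheses.** Hypothesis 1 under PRIMARY HYPOTHESES AND SPECIFIC AIMS has two parts: a fall from baseline at 24 hours, and greater efficacy at 0.5 than at 0.2 mg/kg. JUSTIFICATION also gives the comparison of the lower dose as the reason for having no placebo group. The Hypothesis paragraph of the DATA ANALYSIS PLAN keeps only the first part: "we predict that ketamine infusion compared to baseline will significantly decrease HAM-D scores in PND patient at 24 hrs". It does not separate the doses.

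**Methods named.** The DATA ANALYSIS PLAN opens with "The data analytic strategy will use generalized linear modeling". Its Analysis paragraph adds linear regression for associations with HAM-D improvement (with LOCF), then "A paired t-test was performed to evaluate the key efficacy measure - change from baseline in HAMD total score", and then a secondary paired t-test from baseline to an LOCF endpoint.

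**Sizing.** "For an effect size 1.2, a total of 10 PND patients will be required" in a within-subject design, "with probability 95 % that the study will detect a treatment difference" "at a one-sided 0.05 significance level".

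**Not stated.** The plan does not say whether a row is a patient or an infusion, or which infusion and which baseline enter each paired t-test. It names no patient effect, repeated-measures structure, period term or sequence term, and no test of one dose against the other.

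**The concern.** Two change scores from the same woman are likely to be correlated. The protocol's own background (Clinical studies of Ketamine in depression) cites evidence that response to a first infusion strongly predicted sustained response to later ones. A generalized linear model or linear regression in its plain form, run on infusion-level rows, ignores that correlation. The errors then go in opposite directions:

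- For the overall change from baseline, the standard error is too small and false positives rise.
- For the contrast between doses, the standard error is too large and the precision gained from the crossover is lost.

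Because the efficacy hypothesis in the analysis plan is not split by dose, entering all 20 before-after pairs is one possible reading. With 10 patients and a one-sided test, an open unit of analysis can also be settled after the data are seen. Separately, the second part of Hypothesis 1 has no named test at all.

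**Working it through.** **Inputs from the documents.** 10 patients, 2 infusions each, effect size 1.2, one-sided 0.05, 95% power.

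**Assumed, because the documents give no value.** Correlation ρ between a patient's two changes, taken from 0 to 0.8; equal variances; and, for power only, a dose difference of 0.8 SD of the change score.

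**Step 1: the plan's own figure.** For a one-sided paired t-test with one difference per patient, the noncentrality is d√n = 1.2 × √10 = 3.79 on 9 degrees of freedom. Exact power is 96.7%, and 10 is the smallest n that reaches 95%. The normal approximation ((1.645 + 1.645)/1.2)² = 7.5 gives 8. Exact two-sided testing needs 12. The stated 10 therefore reproduces as one difference per patient, one-sided.

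**Step 2: what stacking 20 rows as independent would do to the standard errors.**

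- Overall change: the true variance of the mean is σ²(1 + ρ)/20 and the naive value is σ²/20. True SE / naive SE = √(1 + ρ). At ρ = 0.5 this is √1.5 = 1.22.
- Dose contrast: the true variance is 2σ²(1 − ρ)/10 and the naive value is 2σ²/10. Naive SE / true SE = 1/√(1 − ρ). At ρ = 0.5 this is 1/√0.5 = 1.41.

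**Step 3: error and power.** These come from 200,000 simulated trials per ρ, one-sided 0.05. Independent rows use 19 degrees of freedom for overall change and 18 for the dose contrast; the paired contrast uses 9.

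| ρ | Overall: true/naive SE | Overall: true error | Dose: naive/true SE | Dose: error, independent rows | Dose: power, independent rows | Dose: power, paired |
|---|---|---|---|---|---|---|
| 0 | 1.00 | 5.1% | 1.00 | 5.1% | 53.0% | 50.2% |
| 0.2 | 1.10 | 6.6% | 1.12 | 3.5% | 53.5% | 58.2% |
| 0.3 | 1.14 | 7.5% | 1.20 | 2.8% | 53.8% | 62.9% |
| 0.5 | 1.22 | 9.2% | 1.41 | 1.4% | 54.3% | 75.4% |
| 0.7 | 1.30 | 10.9% | 1.83 | 0.4% | 55.8% | 91.3% |
| 0.8 | 1.34 | 11.8% | 2.24 | 0.1% | 57.0% | 97.9% |

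A separate run gave 7.5% / 9.1% / 10.8% for overall change at ρ = 0.3 / 0.5 / 0.7. The differences are of the order of simulation error: √(0.09 × 0.91/200,000) is about 0.06 percentage points.

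**Step 4: the same trials with the patient as the unit.** A single infusion per patient, or the mean of her two changes, gives a one-sided error of 4.9% to 5.1% at every ρ. So does the paired dose contrast under no difference.

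**The case against.** A reader might infer that the plan treats 20 infusions as 20 people, so that its standard errors are wrong as written. The documents do not support that, for these reasons:

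- Nothing in the plan says that infusions are pooled or that rows are independent. Its only sizing figure reproduces with the patient as the unit.
- The paired t-test is itself a within-patient method. With one difference per patient it holds its level. It goes wrong only if both infusions enter as separate pairs.
- Generalized linear modelling does not rule out a repeated-measures version such as GEE. The plan is silent on correlation; it does not commit to independence.
- Linear regression is named for associations with improvement, not for the overall effect or the dose comparison, so neither set of figures describes that stated use.
- The wording may be left over from a single-infusion design: Recruitment and Informed Consent describes one study visit, and Alternate plans treats two doses as a later option. A single-infusion analysis would have 10 changes, not 20, and the inflation would not arise.
- The power loss is measured against an unpaired dose comparison that the plan does not contain.

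All of this stands, and it makes the figures conditional. It does not supply what is missing. The trial as designed has two infusions per patient and a dose hypothesis, and the plan gives neither the unit of analysis nor the structure or test that such a design needs.

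**Conclusion.** The concern holds as a gap in method and specification. The named models carry no patient, period or sequence structure, the infusion and baseline entering each paired t-test are not identified, and the dose hypothesis has no within-patient test.

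The size depends on how the gap is filled. With one value per patient there is no error inflation and N = 10 stands. With stacked independent rows, the overall test at a nominal one-sided 5% would run at about 7.5% to 10.8% for ρ of 0.3 to 0.7, and the dose contrast would have about 54-56% power instead of 63% to 91%. At ρ = 0 there is no inflation, and pairing gains nothing (50% against 53%). The power figures also rest on the assumed 0.8 SD difference; the standard-error ratios do not.

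This should be changed before analysis. It does not show that the planned analysis is invalid.

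**What to change.** 1. **HAM-D models and dose contrast.** Replace the plain generalized linear model and linear regression with a linear mixed model: random patient effect; fixed dose, period and sequence terms; small-sample degrees of freedom (for example Kenward-Roger). Name the 0.5 versus 0.2 mg/kg contrast at 24 hours as the test of the second part of Hypothesis 1. A within-patient paired dose contrast serves the same purpose. With complete data it has 10 − 1 = 9 degrees of freedom, or 10 − 2 = 8 if adjusted for period by comparing the two sequences.
2. **Overall change from baseline.** Keep the paired t-test, with one value per patient (n = 10), such as the mean of her two changes, each taken from its own pre-infusion baseline. State that this averages over the two doses and so does not estimate the effect of either one.
3. **Unit and baseline.** For each test, including the secondary LOCF test, state the unit, the infusion or infusions and the baseline used.

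The cost is analysis-plan wording. No extra patients, visits or measurements are needed, the sample-size calculation is unchanged, and the model is standard in the SAS version the plan names.

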breastfeeding mother and the baby. Ketamine and its metabolites will be evaluated in PND patients receiving ketamine 0.5 mg/kg or 0.2 mg/kg at 30 mins, 2 hours and 4-5 hrs after ketamine infusion. All adverse medical and psychiatric events with onset or worsening after the administration of ketamine will be included in the analysis.

The proposed experiment will be a proof-of-concept study in which we will evaluate the safety, pharmacokinetics, and efficacy of ketamine 0.5 mg/kg and 0.2 mg/kg over 40 minutes in a double-blinded and crossover fashion separated over one week (5) (dose used in antidepressant clinical trials) in PND patients who are not currently breastfeeding. The primary outcome measure of efficacy will be the Hamilton Depression Rating Scale (HAM-D-17) at 24 hours and additional secondary anxiety and mood scales. (6). Any adverse medical and psychiatric events will be recorded and summarized. Ketamine and its metabolites will be evaluated at 30 mins, 2 hours and 24 hrs.

Hypothesis 1): Ketamine will significantly decrease (>50%) in HAM-D17 scores at 24 hrs after infusion from baseline. The 0.5 mg/kg dose will be more efficacious than 0.2 mg/kg in improving depression symptoms.

Hypothesis 2) Ketamine will improve anxiety symptoms in PND (as measured using HAM-Anxiety and EPDS) at 24 hrs after infusion in patients with PND. Anxious subtypes are the most common subtype during a late postpartum period representing about 70 % of PND. (40)

Hypothesis 3) Ketamine infusion will be tolerated well by the patients with fewer side effects at 0.2 mg/kg compared to 0.5 mg/kg.

METHODS

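### The named efficacy tests and the 95% power figure fit HAM-D change from baseline; the randomised 0.5 versus 0.2 mg/kg comparison has no named analysis, no sizing and no margin

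*Combined protocol and SAP*

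**What the plan says.** The sizing sentence (DATA ANALYSIS PLAN, Sample size justification) takes an effect size of 1.2 and concludes that 10 patients "will be required for within-subject design with probability 95 % that the study will detect a treatment difference at a one-sided 0.05 significance level". The effect sizes cited are 1.46, from intravenous ketamine in treatment-resistant depression, and 1.2, from brexanolone in perinatal depression (PND).

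The rest of that section is about change from baseline. The hypothesis reads "we predict that ketamine infusion compared to baseline will significantly decrease HAM-D scores in PND patient at 24 hrs". The named test is "A paired t-test was performed to evaluate the key efficacy measure - change from baseline in HAMD total score". A secondary LOCF analysis is again a paired t-test from baseline to endpoint. Two broader statements exist: "The data analytic strategy will use generalized linear modeling", and a linear regression on improvement in depressive symptoms. Neither mentions dose, period or sequence.

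The design is a two-dose crossover. METHODS (Research Design and Methods) gives 0.5 or 0.2 mg/kg "in a double-blinded and crossover fashion separated by minimum 7 days, with the order being randomized and balanced across subjects", with "a second infusion visit where they will receive the infusion that was not given on the first visit". The stated purpose is "Two doses will help decide the safe, tolerable and effective dose for PND". Hypothesis 1, under PRIMARY HYPOTHESES AND SPECIFIC AIMS, adds to the baseline prediction: "The 0.5 mg/kg dose will be more efficacious than 0.2 mg/kg in improving depression symptoms". The JUSTIFICATION section defends having no placebo arm by saying that the aim is to learn whether a lower dose matches the higher one on efficacy with fewer side effects.

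**The concern.** Randomisation in this trial determines only the order of the two doses. The contrast that it supports directly is the within-patient 0.5 minus 0.2 mg/kg difference, and that is the contrast for which the analysis section names no method. An analyst who ran only the named tests would report change from baseline and would never estimate the dose difference.

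The plan also states two different dose objectives. Hypothesis 1 predicts superiority of the higher dose. The JUSTIFICATION asks whether the lower dose does as well, which is a non-inferiority or equivalence question and needs a margin. None is given. If the dose comparison were added after the data were seen and came out non-significant, nothing in the plan would prevent that from being read, next to a 95% power statement, as support for the lower dose.

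**Working it through.** **Inputs from the documents.** N = 10; effect size 1.2; one-sided alpha 0.05; power 95%; within-subject design (Sample size justification). Dose order randomised and balanced (METHODS), so 5 patients per order. No dose difference, SD of the dose difference, or margin is given.

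**1. The plan's own figure.** For a paired t-test, power = P(T > t(0.95, n−1)), where T is noncentral t with n−1 df and noncentrality d√n. At n = 10 and d = 1.2, the noncentrality is 1.2 × √10 = 3.79 and the critical value is t(0.95, 9) = 1.833.

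| n | Power, d = 1.2, one-sided 0.05 |
|---|---|
| 8 | 91.9% |
| 9 | 94.8% |
| 10 | 96.7% |

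Ten is the smallest n that reaches 95%, so the figure reproduces. Two independent groups would need 16 per arm, so the calculation is a paired one.

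**2. Which contrast it covers.** The arithmetic alone cannot say, because any paired contrast with a standardised effect of 1.2 gives the same N. The context can: the hypothesis and the named tests are against baseline, neither cited effect size is presented as a difference between two ketamine doses, and one source listed for the 1.2 is titled as an open-label study. Since each patient has two infusions, the sentence still leaves open which infusion or dose is meant.

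**3. What 10 patients give for the dose comparison.** Let dz be the mean within-patient dose difference divided by its SD. With 5 patients per order and a period term, the standard error of the dose difference is SD/√10 on 8 df. A simple paired analysis has the same standard error on 9 df.

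- 95% CI half-width with period fitted: t(0.975, 8)/√10 = 2.306/3.162 = 0.73 SD.
- 95% CI half-width, simple paired: t(0.975, 9)/√10 = 2.262/3.162 = 0.72 SD.
- dz for 80% power, by the formula in step 1 with the stated df: one-sided 0.86 (8 df) or 0.85 (9 df); two-sided 1.01 (8 df) or 1.00 (9 df).

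**4. Power over an assumed range.** The documents give no value for dz, so these rows are illustrations (n = 10, 8 df).

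| Assumed dz | One-sided 0.05 | Two-sided 0.05 |
|---|---|---|
| 0.3 | 22% | 13% |
| 0.5 | 42% | 29% |
| 0.8 | 75% | 60% |
| 1.0 | 89% | 79% |
| 1.2 | 96% | 91% |

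**5. Reading a null result.** If the observed dose difference were exactly zero, the 95% CI would run from −0.73 to +0.73 SD of the within-patient difference. With no margin there is nothing to compare those limits with.

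**The case against.** The strongest reply is that the text explains itself. The sentences after the sizing statement predict and test change from baseline, and the JUSTIFICATION gives the safety and efficacy of ketamine as the primary goal. That stands: the wording of the sizing sentence is a matter for clarification, and only the infusion or dose that it covers is really open.

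A second reply is that the study calls itself proof-of-concept and a pilot, so an unsized dose comparison is acceptable. That also stands, provided the plan says so. It does not excuse leaving the comparison without a named analysis.

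Stronger readings are tempting, and the documents do not support them:

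- *The sample size is wrong.* It is not; it reproduces for the contrast that the section tests.
- *The trial is underpowered for dose.* No dose difference or SD is given, and the illustrative range runs from 22% to 96% one-sided.
- *The sponsor will treat non-significance as equality.* Nothing in the analysis section says so. The risk comes from a stated aim that has no margin.
- *The 1.2 is on the wrong scale.* That depends on cited sources that are not in the documents, so it is a query and not a finding.

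A last caution is that a dose estimate should not look cleaner than the design allows. HAM-D is scheduled at screening and before each infusion, so the baseline for the second period needs defining. The minimum gap is 7 days, while the protocol's own background reports response lasting to one week in up to 35% of patients with treatment-resistant depression. Both points stand and are carried into the fix.

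**Conclusion.** The point holds as a gap in the analysis plan. The 95% power figure is correct for HAM-D change from baseline if 1.2 is a standardised within-patient change. The randomised 0.5 versus 0.2 mg/kg comparison has no named analysis, and the plan's superiority hypothesis and its lower-dose aim are different questions with no margin for the second. Power for the dose contrast is unknown. What can be stated is its precision: a 95% CI half-width of about 0.73 SD of the within-patient difference, assuming all 10 patients complete both periods, 5 per order, with roughly normal differences and no carry-over. On those terms a non-significant result cannot support the claim that the lower dose does as well. This should be corrected before analysis; it gives no reason to change the sample size.

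**What to change.** Keep N = 10. In the DATA ANALYSIS PLAN:

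1. Say that the 95% refers to change from baseline in HAM-D-17 at 24 hours, name the infusion or dose covered, and say that it does not refer to the dose comparison.
2. Add text along these lines:

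> The within-patient 0.5 minus 0.2 mg/kg difference in HAM-D-17 change at 24 hours, with change measured from a pre-specified baseline (for example the same-day pre-infusion score), will be estimated from a crossover model with dose and period and reported with a two-sided 95% CI. With 10 patients the half-width is about 0.73 SD of the within-patient difference (0.72 for a simple paired analysis), and 80% power requires a standardised difference of about 0.86 (one-sided 0.05) or 1.0 (two-sided 0.05). The comparison was not sized. A non-significant difference will not be read as equal efficacy. Pre-infusion scores in the two periods will be compared and possible carry-over acknowledged.

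3. Reconcile the superiority wording of Hypothesis 1 with the lower-dose aim in the JUSTIFICATION, or state that the second is descriptive only.

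As a separate query, ask the sponsor to confirm that the 1.2 is in SDs of within-patient change; if it is not, the power statement should be restated.

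The cost is a few sentences and one check of a source, with no extra patients, visits or data. The dose result will carry a wide interval, and the period term costs one degree of freedom (0.73 against 0.72 SD).

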Study Population: We will enroll 10 patients with Perinatal Depression (PND) in this study. Participants will be female adults, aged 18-45 years, who meet the criteria for PND. Participants will be recruited without regard to race, religion or ethnicity. Participants will be postpartum and no longer breastfeeding or will be willing to stop breastfeeding during the study. Participants will be recruited through flyers and clinic referrals in the Houston area. Women of all ethnic backgrounds will be recruited to participate. It is anticipated that the subject demographic profile will closely mirror the larger population of individuals with PND from which they are recruited. We will do so by posting flyers at community medical clinics, outpatient mental health clinics and local business in the area

Inclusion Criteria:

- 1) Female subjects, ages 18-45 years
- 2) Experienced a major depressive episode in the postpartum period beginning within the first 4 weeks following delivery and with moderate or severe symptoms (>12 EPDS or >14 HAM-D).
- 3) No or partial response to adequate doses of SSRI medications to treat PND for longer than 6 weeks.
- 4) PND patients will be requested to maintain a stable dose of antidepressants while enrolled in the study trial.
- 5) Patients that can speak and read the English language are able to understand the study procedures and sign the informed consent

Exclusion Criteria:

- 1) No current or past psychosis or severe personality disorder.
- 2) No current substance abuse or dependence.
- 3) No serious and imminent suicidal or homicidal risk.
- 4) No recent or history of major and unstable medical problems that affect brain anatomy, neurochemistry, or function.
- 5) Not diagnosed with cardiovascular disorders.
- 6) No increased risk of laryngospasm or active upper respiratory infections.
- 7) Not diagnosed with intellectual disability or neurodegenerative diseases.
- 8) Mothers that are currently breastfeeding.
- 9) No current pregnancy.

Clinical and diagnostic assessments:

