Once eligible for the study screening visit, they will be invited for study Day #1, which will begin with the presentation of the informed consent form. The consent form will detail the requirements of study participation (e.g., # of visits, type of data collected, time commitment, etc.) Subjects will be told that the purpose of the study is to evaluate neurophysiological measures to study the effect of ketamine on PND. Subjects will be informed that they will have to attend a total of 2 visits (screening/baseline and 1 study visit) and 2 follow up phone calls. Other information on the consent form will include a full description of study requirements, reimbursement, risks, benefits, alternatives, and the role of the local IRB. All questions will be answered before written consent is requested. Informed consent will be obtained only by the PI or a trained senior member of the staff (e.g. study coordinator).

The research protocol, consent form, and all assessment/advertising materials will be reviewed and approved by the Committee for the Protection of Human Subjects (CPHS) at UTH.

Protections against risk

- 1 **Risks related to diagnostic procedures/questionnaires:** As noted above, the primary risks related to these procedures are participant discomfort and loss of confidentiality. Regarding participant discomfort, we will make clear that we ask for this sensitive information as part of the consent process. Further, while subjects may be uncomfortable reporting these issues, the risks of serious sequelae are extremely low. Regarding confidentiality, we have rigorous procedures in place to ensure confidentiality of data.

including locked cabinets for confidential files, participant coding, secure computer systems, and rigorous training of personnel. Computer systems are secure and strictly monitored by University IT staff. Laboratory staffers are trained in confidentiality of participant information. No information is allowed to leave the lab or to be accessed by a computer outside of the university's secure computer system, and all data are further protected by permissions and passwords given only to necessary research personnel. No information will be published in a form in which the participant can be identified. We will also obtain a Certificate of Confidentiality for this study to provide additional protection for sensitive information.

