JUSTIFICATION - Research in PND is of critical importance due to its substantial burden on mother, family and child's emotional, cognitive and behavioral development. Rapid and effective treatment of severe PND is a significant unmet need. The primary goal of the project is to evaluate the safety and efficacy of sub-anesthetic antidepressant dose ketamine treatment in severe PND patients. This proposal will be the first systematic investigation of ketamine's antidepressant effect in PND. The study design is simple and robust that can provide

early treatment response signal without significant additional discomfort for patients. The results from this pilot proposal could potentially yield critical information regarding markers of treatment response in PND - a potentially high impact research area. the

Having a placebo group in this research project would not be warranted at this place since the aim is to determine if a lower ketamine dose would be as effective and with lower side effects for PND patients.

Data Handling and Record Keeping

This study will acquire, use and create individually identifiable health information (known as Protected Health Information or PHI). Confidentiality will be protected at all times by having research records identified by code number only. All research information will be stored in locked files at all times. Only authorized research staff will have access to the information gathered in this study. Only subjects capable of providing consent will be included in the study.

As per the Health Insurance Portability and Accountability Act (HIPAA), all individuals who are eligible and agree to participate in this research study will be required to sign a HIPAA research authorization prior to participation. If an individual refuses to sign the HIPAA research authorization, they will not be able to participate in this study. The HIPAA form is part of the official consent form.

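### The planned efficacy test is an uncontrolled change from an undefined baseline, so its 5% error covers only zero change, while the randomised dose comparison has no named test

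*Combined protocol and SAP*

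**What the plan says.** The Data Analysis Plan predicts that "ketamine infusion compared to baseline will significantly decrease HAM-D scores in PND patient at 24 hrs". The named test follows the same line: "A paired t-test was performed to evaluate the key efficacy measure - change from baseline in HAMD total score". The secondary version with last observation carried forward is again a paired t-test of change from baseline. The sample size is built on this comparison: "For an effect size 1.2, a total of 10 PND patients will be required for within-subject design with probability 95" per cent, "at a one-sided 0.05 significance level", and the plan describes what is detected as a treatment difference.

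No inert comparator exists, and the Justification section defends this: "Having a placebo group in this research project would not be warranted", because the aim there is to compare a lower with a higher dose. That comparison is randomised, double-blind and crossover (Research Design and Methods), and Hypothesis 1 predicts that 0.5 mg/kg will outperform 0.2 mg/kg. The Data Analysis Plan names no test and gives no power for it.

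The Data Analysis Plan does not say which score is the baseline. Two other places bear on it:
- Recruitment and Informed Consent says that subjects will "attend a total of 2 visits (screening/baseline and 1 study visit" (plus phone calls), which joins screening and baseline.
- The assessment schedule marks HAM-D-17 at screening and again before each infusion.

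Entry requires a depressive episode "with moderate or severe symptoms (>12 EPDS or >14 HAM-D". The gap from screening to infusion is open: "Extension of the timeline can occur depending on the time between the screening visit and the first infusion dose", within a 3-month total.

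**The concern.** A paired t-test of change asks whether the mean change is zero. Without any drug effect the mean change need not be zero. Women enter because they scored high, their depression may improve with time, and every participant knows that both infusions contain ketamine, because the blind conceals only the dose. Improvement from any of these sources enters the test as if ketamine had caused it.

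A significant fall could then be reported as antidepressant efficacy at a 5% error rate when the 5% refers to a different null hypothesis. The comparison that randomisation does protect would meanwhile be left without a planned analysis. An undefined baseline makes matters worse: the choice can be made after the data are seen, and a screening baseline brings in more non-drug change than a pre-infusion one.

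**Working it through.** **Inputs from the documents.** Effect size 1.2, n = 10, one-sided 0.05, 95% power, within-subject (Data Analysis Plan). Entry at EPDS >12 or HAM-D >14 (Inclusion Criteria). At least 7 days between infusions (Research Design and Methods). Up to 35% still responding at one week (Aims).

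**Assumed, because the documents give no figure.** SD of HAM-D change 4, 6 or 8; non-drug fall 2 or 3 points.

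**Step 1: reproduce the sample size.** Power of the paired t-test is P(T > t₀.₉₅,₉), with T noncentral t, df = n − 1 = 9 and noncentrality d√n. Here d√n = 1.2 × √10 = 3.79 and the critical value is 1.833, so power is 96.7%. Ten is the smallest n that reaches 95%. The arithmetic is right for the null of zero mean change.

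**Step 2: chance of significance with no ketamine effect.** Same formula, with d = non-drug fall / SD of change.

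| Non-drug fall | SD 4 | SD 6 | SD 8 |
|---|---|---|---|
| 0 points | 5% | 5% | 5% |
| 2 points | 43% (d = 0.50) | 25% (d = 0.33) | 18% (d = 0.25) |
| 3 points | 71% (d = 0.75) | 43% (d = 0.50) | 29% (d = 0.375) |

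Simulation with 200,000 trials gave 18.0% at d = 0.25 and 42.7% at d = 0.50, in agreement.

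**Step 3: what a screening baseline could add.** Regression to the mean is (1 − ρ) × (E[X | X > cut] − μ), with X normal and the cut at 14.5 to represent HAM-D >14. For an assumed unselected mean of 14 to 20, SD 4 to 6 and retest correlation 0.6 to 0.9, the fall is about 0.1 to 2.0 points. Taking the SD of change from the same model, this alone lifts the 5% to about 6% to 34%. The model treats everyone as selected on HAM-D. A woman who qualifies on EPDS alone is selected on HAM-D only indirectly, so her regression is smaller.

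**Step 4: the randomised contrast.** For a period-adjusted two-sequence crossover with five women per sequence, df = 8 and the noncentrality is d√10, where d is the dose difference divided by the SD of the within-patient difference. With a common non-drug shift and a period effect added, simulated significance under no dose difference was 4.9% to 5.0%, assuming no carry-over. Power at n = 10, one-sided 0.05:

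| Dose difference | Power |
|---|---|
| 0.5 SD | 42% |
| 0.8 SD | 75% |
| 0.86 SD | 80% |
| 1.2 SD | 96% |

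**The case against.** The protocol calls itself a proof-of-concept and a pilot, and it gives a reason for having no placebo. That excuses a small uncontrolled study. It does not make a fall within patients an efficacy result, and the reason given rests on the dose comparison that the plan does not test. The plan's general reference to generalized linear modelling could accommodate a dose term, but none is named.

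Hypothesis 1 predicts a fall of more than 50%, which from a HAM-D of 15 means more than 7.5 points, well above the non-drug falls used here. This has force for interpretation, and a fall of that size would be harder to explain away. But the t-test does not test it. Significance needs an observed mean fall of only 1.833/√10 = 0.58 SD: 2.3, 3.5 or 4.6 points for SD 4, 6 or 8.

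Recovery between screening and infusion may be limited. Women must have had no or only partial response to more than 6 weeks of SSRI treatment, they are asked to keep a stable dose, and eligibility is reviewed before each infusion. If severity is re-checked at that review, the pre-infusion score is itself selected, so a same-day baseline would not remove all regression to the mean. These points stand and are why no single figure is given for the bias.

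A reader might infer that the protocol sets baseline equal to screening. The documents do not support that. It rests on one parenthesis in a consent description that counts one study visit where the design has two infusions, and a pre-infusion HAM-D-17 is scheduled. The accurate statement is that baseline is undefined.

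**Conclusion.** The point holds for either baseline: the stated 5% and 95% refer to zero change, and an uncontrolled fall cannot separate ketamine from expectancy, recovery or regression to the mean. With a non-drug fall of 2 to 3 points, the chance of a significant result without any drug effect is 18% to 71% across SDs of 4 to 8. Both the fall and the SD are assumptions, so the table shows sensitivity and does not estimate this trial's error rate. The extra bias from a screening baseline is of uncertain size.

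The sample-size arithmetic is not at fault, and nothing here shows that a fall in HAM-D would be non-drug. The weakness lies in the conclusion that the test can carry and in the absence of a planned test for the randomised comparison.

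**What to change.** In the Data Analysis Plan:

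1. Define baseline as the HAM-D-17 taken before infusion on the same infusion day. Note that the value before infusion 2 may carry residual effect, given up to 35% still responding at one week and a minimum gap of 7 days.
2. State that change from baseline is descriptive and supports only the conclusion that HAM-D fell after infusion. Restate the 95% power as power to detect a change from baseline.
3. Name the within-patient contrast of 0.5 with 0.2 mg/kg on HAM-D-17 at 24 hours, adjusted for period, as the randomised efficacy comparison. Report its precision at n = 10: about 42% power for a 0.5 SD difference, and 80% only at about 0.86 SD. State that these figures assume no carry-over.

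This uses only scheduled data and adds no patients. The cost is a more modest permitted conclusion. The contrast compares doses, not ketamine with nothing, so similar results at both doses would leave efficacy against no treatment unanswered, and the plan should say so.
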